**Collect normative data for pancreatic stiffness as measured by MR elastography.**

*Hypothesis 2.* Pancreatic parenchymal stiffness in the pediatric population will fall in a normative range similar to adult norms and will not depend on subject age or size. *Exp 2.* Pancreatic parenchymal stiffness will be measured in the same healthy cohort of 50 healthy pediatric subjects including 25 subjects ages 6-11.9 years and 25 subjects 12-15.9 years.

**Assess the relationship between pancreatic exocrine function, pancreatic stiffness and pancreatic parenchymal volume.** *Hypothesis 3.* Pancreatic exocrine function as measured by MR-PFT and pancreatic stiffness as measured by MRE will be dependent on pancreatic parenchymal volume. *Exp 3.* Secreted fluid volumes as measured by MR-PFT and pancreatic

stiffness as measured by MRE will be correlated with volumetric measurements of pancreatic parenchymal volume.

**Assess the effect of secretin on the visibility of the pancreatic duct.** *Hypothesis 4.* A subjective, blinded assessment of pancreatic duct visibility pre-and post-secretin will show an increase in visibility on post-secretin images.

We will also store this data to identify normative values in controls for pancreatic and any other gastrointestinal parameters in MRCP.

*Significance and Innovation:*

Our study will add significant information to the existing literature regarding diagnosis and staging of CP, and will set the foundation for using MR as a non-invasive biomarker for CP/PI in pediatrics. Our study is novel because it will investigate the use of MRI for assessing pancreatic anatomy, function, and stiffness in the pediatric population. It will also shed light on gastrointestinal anatomy and function in pediatric healthy controls which has not yet been described in the literature. Moreover, the results of our study will fill a knowledge gap regarding normal secretory function of the pancreas in children.

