In preparation for this study, we developed a protocol to measure pancreatic fluid volume secreted in response to secretin administration, confirmed feasibility of pancreatic stiffness measurements by MRE and analyzed our experience with MR in pediatric patients with pancreatic disease, primarily CP. We have a cohort of CP patients that have undergone MRCP with the proposed study protocol and we will continue to collect data on CP patients that undergo MR studies. The overall aim of this pilot-study is to collect MR-PFT and MRE data in a small group of normal pediatric subjects (with no history of pancreatic disease, CP/PI, or intestinal disease) to serve as a preliminary data set for a subsequent comparative study of MR-PFT and MRE in children with CP. The ultimate aim is to provide results that would position non-invasive MR studies as an accurate, sensitive, and specific alternative to standard modalities of CP diagnosis and therapy monitoring (endoscopic PFT (ePFT), endoscopic

retrograde cholangiopancreatography (ERCP), endoscopic ultrasound (EUS), and biopsy). **Our overall hypothesis is that normative ranges can be established for total secreted pancreatic fluid volume as measured by MR-PFT and for pancreatic stiffness as measured by MRE and that secreted volumes but *not* pancreatic stiffness will depend on subject age and size.**

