**DATA ANALYSIS/METHODS:**

*Statistical analysis:*

Statistical analyses will be tailored to our study purposes as follows:

**Collect normative data for volume of secreted fluid in response to secretin administration in a representative sample of healthy pediatric controls.**

Means, standard deviations and 95% confidence intervals will be used to summarize study population secreted volumes. Linear regression will be used to assess for significant correlation between subject age and secreted volume. Similar regression models will be used to test other body-size covariates such as BSA, BMI, etc. If feasible, a quantile regression will be performed of secreted volume or BSA normalized secreted value to attempt to quantify normal range as a function of age, BMI, etc.

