**Collect normative data for pancreatic stiffness as measured by MR elastography.**

Means, standard deviations and 95% confidence intervals will be used to summarize study population pancreatic parenchymal stiffness. Linear regression will be used to assess for significant correlation between subject age and parenchymal stiffness. Similar regression models will be used to test other body-size covariates such as BSA, BMI, etc.

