**Assess the effect of secretin on the visibility of the pancreatic duct.**

Frequencies and rankings will be compared with Fischer exact test and Wilcoxon rank sum tests to compare visualization of the pancreatic duct pre- and post-secretin.

*Power calculation:*

To establish relationship between secreted fluid volume and subject body size or age, we base a power calculation on analysis of MR-PFT data in 19 CP patients and the assumption that secreted volume is correlated with age in this sample of patients. In a linear regression analysis of these patients, the observed residual standard error is approximately 39, with an  $R^2 \sim 0.40$ . The observed regression coefficient is 5.274, and standard deviation of predictor age is  $\sim 5.816$ . If this holds in a general population, we require at least 15 normal subjects to have a significant regression coefficient at 0.05 level, and 80% power.

Additionally, from the previously reported study of normal adult patients by Mensel et al. [25], the coefficient of variation (CV) of secreted volume (TEV in the paper) at various time points from secretin injection ranged from 0.30 to 0.51. Given that we plan to enroll subjects in two age groups (6-11.9 and 12-15.9 years old), 25 subjects in each age group will provide 80% chance that the 95% confidence interval of mean secreted volume will be within 12% to 20% of the mean value, depending on the actual CV observed.

Therefore, we plan to enroll a total of 50 evaluable subjects in the study to meet both needs above.

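### Hypothesis 2 says stiffness does not depend on age or size, but the plan only tests for a significant slope, and a non-significant result would not establish that

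*Combined protocol and SAP*

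**What the plan says.** Under PURPOSE OF STUDY, Hypothesis 2 states that stiffness in children "will fall in a normative range similar to adult norms and will not depend on subject age or size". The overall hypothesis at the end of BACKGROUND repeats the second half as a contrast: "secreted volumes but *not* pancreatic stiffness will depend on subject age and size". The same section describes a pilot whose data are "to serve as a preliminary data set for a subsequent comparative study of MR-PFT and MRE in children with CP".

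Under DATA ANALYSIS/METHODS, the stiffness paragraph contains three statements:

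- a summary: "Means, standard deviations and 95% confidence intervals will be used to summarize study population pancreatic parenchymal stiffness";
- the age analysis: "Linear regression will be used to assess for significant correlation between subject age and parenchymal stiffness";
- the size analyses: "Similar regression models will be used to test other body-size covariates such as BSA, BMI, etc".

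For secreted volume, the plan adds that, if feasible, "a quantile regression will be performed of secreted volume or BSA normalized secreted value to attempt to quantify normal range" by age, BMI and similar variables. Nothing comparable is planned for stiffness.

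The Power calculation section gives a regression sample size and a precision statement, both for secreted volume, and concludes: "Therefore, we plan to enroll a total of 50 evaluable subjects in the study to meet both needs above".

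**The concern.** Hypothesis 2 has two parts. The comparison with adult norms is not at issue here. The independence part is a claim of no effect, and it is paired with a test designed to find an effect. The plan can therefore contradict this part of the hypothesis but has no criterion for supporting it. The confidence intervals it mentions describe stiffness in the study population, not a slope. No trend is defined as too small to matter, and the documents do not say how a non-significant result will be read.

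The study's product is normative data. Because a range that varies with age and size is contemplated only for secreted volume, whether one stiffness range can serve all ages rests on this question. A later comparative study would need to know how large an age or size trend remains possible, and a statement that the slope was not significant does not tell it.

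**Working it through.** **The plan's own regression figure.** The only regression sample size is for secreted volume on age: slope 5.274, SD of age 5.816, residual standard error 39, significance level 0.05, 80% power, at least 15 subjects. The noncentrality is 5.274 × 5.816 × √15 / 39 = 3.05 on 13 degrees of freedom. Two-sided power is 80.4%, so 15 reproduces. It says nothing about stiffness.

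**Inputs for stiffness.** From the documents: N = 50, with 25 children aged 6–11.9 and 25 aged 12–15.9. Assumed: ages uniform within each band, which gives mean age 11.45 and age SD 2.887; a range of 2.6 to 3.2 is also shown. The documents give no stiffness SD, so results are in units of the residual SD, σ. Tests are two-sided at 0.05 on 48 degrees of freedom, t = 2.011.

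**Precision.** The standard error of the change over 9.9 years (age 6 to 15.9) is 9.9σ / (2.887 × √50) = 0.485σ. The 95% half-width is 2.011 × 0.485σ = 0.975σ (1.083σ at age SD 2.6; 0.880σ at 3.2). An estimated slope of zero would thus leave changes of nearly one residual SD in either direction open. For any covariate, including body size, the half-width per 1 SD of the covariate is 2.011σ / √50 = 0.284σ.

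**Power of the planned test** (noncentral t, noncentrality = true change / 0.485σ):

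| True change, age 6 to 15.9 | Chance of significance |
|---|---|
| 0.5σ | 17% |
| 1.0σ | 52% (44% at age SD 2.6; 61% at 3.2) |
| 1.5σ | 86% |
| 2.0σ | 98% |

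On the correlation scale, a true correlation of 0.3 is missed 41% of the time and one of 0.2 is missed 71% of the time.

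**What an undetected 1.0σ rise could do.** Assume one upper limit of mean + 1.96 SD for all ages; the documents do not define range limits. The pooled SD is √(1 + (2.887/9.9)²) = 1.042σ, so the limit lies 1.96 × 1.042 = 2.042σ above the overall mean.

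- At age 6 the mean is shifted by (6 − 11.45)/9.9 = −0.551σ, and P(Z > 2.592) = 0.5%.
- At age 15.9 it is shifted by (15.9 − 11.45)/9.9 = +0.449σ, and P(Z > 1.592) = 5.6%.

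The nominal figure is 2.5% at every age.

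**What 50 children can support if stiffness truly does not change with age** (simulation, age SD 2.887). Let X be the 95% confidence limit furthest from zero. Its median is 1.30σ (1.45σ at age SD 2.6; 1.18σ at 3.2), and it exceeds 1.60σ in one study in five. The chance that the interval falls wholly inside a negligible range is:

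| Negligible range | 90% interval inside | 95% interval inside |
|---|---|---|
| ±1.0σ | 30% | 9% |
| ±1.25σ | 63% | 43% |
| ±1.45σ | 81% | 67% |

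**The case against.** The strongest reply is that the documents never say a non-significant slope will be taken as proof of independence. Testing for a slope is a legitimate way to challenge the hypothesis, and any linear regression produces a slope and standard error, from which the interval follows. The same wording is used for secreted volume. The study is a descriptive pilot, so an equivalence standard would ask more than it claims.

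The harm figures also rest on choices made for illustration. A 1.0σ change corresponds to a correlation of about 0.28, or about 8% of stiffness variance, and power is already 86% at 1.5σ. Even with no age trend, an upper limit of mean + 1.96 SD estimated from 50 children would have a true exceedance of roughly 0.7% to 7%, about as wide as the 0.5% to 5.6% shown above.

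Most of this is fair, and it limits the consequence. The missing element is a decision criterion and a reporting commitment, not data or a model. Sizing a pilot on secreted volume alone is not an error. Sampling error in a limit is indeed of similar size, although a trend differs in kind: it misplaces the limit in opposite directions for younger and older children. But none of this makes a null p-value evidence of no dependence. The hypothesis is stated twice as a no-effect claim, and the text offers no way of supporting it. Pilot status argues for estimation as the remedy, not for leaving the test as it stands.

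**Conclusion.** The concern holds. As written, the plan can refute the independence part of Hypothesis 2 but cannot support it. At N = 50 the test is about as likely as not to miss a 1.0σ change across the studied ages, and a zero estimate leaves about ±0.98σ open. It is informative against large trends, with about 98% power at 2.0σ. These figures assume uniform ages within the two bands and are in residual SDs because no stiffness SD is given; the logical point needs neither assumption. No enrolment, safety or data-collection decision depends on it. The plan should be amended, but the change is modest.

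**What to change.** Add to the stiffness paragraph of the statistical analysis:

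> Slopes of stiffness on age and on each body-size covariate will be reported with 95% confidence intervals, expressed as the change in kPa over ages 6 to 15.9 years and over the observed range of each size measure. A non-significant p-value will not be read as independence.

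Then choose one of two courses, and align Hypothesis 2 and the overall hypothesis with it:

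- **(a) Estimation.** Restate the independence part as an estimation aim, and report that dependence was not detected and that changes up to X kPa are not excluded, X being the 95% limit furthest from zero.
- **(b) Equivalence.** Claim no meaningful dependence only if the 90% confidence interval (two one-sided 5% tests) lies within a negligible range in kPa fixed before analysis.

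Option (a) is the more realistic with 50 children. Option (b) requires the sponsor to justify a kPa range that the documents do not give, and the chances of success shown above are modest unless that range is wide.

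The cost is close to nil: wording in three places, with the same data and regressions. The real price is that the study may be unable to claim independence, since even with no true age trend X would be about 1.30σ in the median study.

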**Assess the relationship between pancreatic exocrine function, pancreatic stiffness and pancreatic parenchymal volume.**

Linear regression will be used to define correlation between pancreatic parenchymal volume and secreted fluid volume in response to secretin administration.

For the stored anatomy and other gastrointestinal functional data from the controls, we will conduct statistical analyses according to the purpose of the question that is asked from this data, for instance for pancreatic volume measurements, we will conduct a comparison analysis

by t test, ANOVA, Wilcoxon test and other measures to fit the purpose of the other future studies.

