**PURPOSE OF STUDY:**

**Collect normative data for pancreatic state (the size, volume, anatomy, biliary and vascular structures) as well as the volume of secreted fluid in response to secretin administration in a representative sample of healthy pediatric controls.**

**Determine secreted volumes:** *Hypothesis 1.* Total secreted fluid volume as measured by MR-PFT will correlate with subject size and age. *Exp 1.* MR-PFT will be performed in 50 healthy pediatric subjects including 25 subjects ages 6-11.9 years and 25 subjects 12-15.9 years. Secreted volumes will be correlated with subject age and height, weight, body mass index and body surface area.

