#### *Secretin:*

Synthetic human secretin is a peptide hormone with an amino acid sequence identical to naturally occurring secretin. The main action is to increase the secretion of pancreatic juice, including bicarbonate by stimulating the exocrine pancreas thereby assisting in the diagnosis of exocrine pancreatic dysfunction. Secretin is FDA approved for pancreatic stimulation use in adults. We regularly use secretin in clinical practice at CCHMC. A limited MRCP with secretin stimulation with a dose of 0.2 mcg/kg (maximum of 16 mcg) will be performed and post-processed as detailed below.

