### **RECRUITMENT & CONSENT OF PARTICIPANTS:**

*Subject Recruitment:*

Recruited subjects will have no history of pancreatic disease and will be identified through review of patients presenting for non-abdominal imaging examinations. Patients presenting for musculoskeletal MRI examinations will likely be the major source for recruited patients. In the last 2 years, 1297 musculoskeletal MR examinations have been done in pediatric patients, ages 6 -15 years, at our institution, providing a ready source for recruitment. Subjects may additionally be recruited through public recruitment using existing clinical trial recruitment services at CCHMC, including advertising within our institution to raise awareness of the study. CCHMC employees may be invited to enroll their children in the study; they would be invited by the research coordinator. Subject charts will be reviewed for evidence of pancreatitis or other pancreatic disease prior to/during enrollment. Following initial screening, subjects will be contacted by the study coordinator or an investigator and enrolled after informed consent is obtained. During enrollment, absence of exclusion criteria will be confirmed with a questionnaire completed prior to imaging.

50 evaluable subjects will be recruited evenly divided as follows:

25 subjects age 6-11.9 years

25 subjects age 12-15.9 years

*Inclusion Criteria:*

1. Subjects between the ages of 6 and 15.9 years.
2. Subjects without a documented history of (or suggestive of) pancreatic disease.

*Exclusion Criteria:*

1. History of pancreatic disease, liver disease, intra-abdominal neoplasm, abdominal inflammatory process such as inflammatory bowel disease (IBD), or systemic illness that may affect pancreatic state (e.g. cystic fibrosis).
2. Subjects with surgical hardware/implanted devices making them ineligible for MRI (e.g. pacemaker or other implanted medical device not approved for MRI).
3. Subjects who require any form of sedation or general anesthesia for MRI.
4. Subjects unable to breath-hold for the required 15-20 second imaging sequence.
5. Subjects who are pregnant or less than 12 months post-partum.

*Process of obtaining Consent:*

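### The planned analysis of Hypothesis 3 has no size-adjusted model, so it cannot separate dependence on gland volume from shared growth; the stiffness half also lacks a stated method

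*Combined protocol and SAP*

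**What the plan says.** In PURPOSE OF STUDY, Hypothesis 3 covers two outcomes: "Pancreatic exocrine function as measured by MR-PFT and pancreatic stiffness as measured by MRE will be dependent on pancreatic parenchymal volume". Exp 3 commits to relating both to gland volume. For the second outcome it says that "stiffness as measured by MRE will be correlated with volumetric measurements of pancreatic parenchymal volume", without naming a method.

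The matching part of DATA ANALYSIS/METHODS names stiffness in its heading but plans a single regression: "Linear regression will be used to define correlation between pancreatic parenchymal volume and secreted fluid volume in response to secretin administration". It lists no covariate. The rest of that sub-section concerns stored data for future questions. The stiffness sub-section just before it relates stiffness to age and body size, not to gland volume.

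Elsewhere the plan expects secretion to follow growth. Hypothesis 1 reads "Total secreted fluid volume as measured by MR-PFT will correlate with subject size and age". The overall hypothesis in BACKGROUND is that secreted volumes, but not stiffness, "will depend on subject age and size". Eligibility spans a period of rapid growth: "Subjects between the ages of 6 and 15.9 years". Normalisation to body surface area (BSA) appears only in an optional analysis of the normal range: "If feasible, a quantile regression will be performed of secreted volume or BSA normalized secreted value to attempt to quantify normal range".

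**The concern.** Hypothesis 1 makes body growth a driver of secreted volume. If gland volume also increases with growth, the two volumes will correlate across children aged 6 to 15.9 even when a larger gland adds nothing at a given age and size. A positive single-predictor slope could then restate Hypothesis 1 and still be reported as support for Hypothesis 3.

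The Secretin section adds a further possible route from body size to secretion, because the stimulus itself scales with weight: "A limited MRCP with secretin stimulation with a dose of 0.2 mcg/kg (maximum of 16 mcg) will be performed".

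At stake is how the result is read. These data are meant to support a later comparison with children who have chronic pancreatitis (CP). Whether secretion tracks the gland or merely the child affects what later patients' values should be compared with.

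**Working it through.** **The plan's own figure.** The Power calculation section gives slope 5.274, age SD 5.816 and residual standard error 39, from 19 CP patients.
- Explained SD: 5.274 × 5.816 = 30.67, squared 940.9. Residual variance: 39² = 1521.
- R² = 940.9 / (940.9 + 1521) = 0.382, close to the stated 0.40.
- A noncentral F test of one slope at two-sided 0.05, with noncentrality N × R²/(1 − R²), gives N = 15 (power 0.804). With R² = 0.40 it gives N = 14 (power 0.801).

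The stated minimum of 15 is reproduced. It concerns secreted volume on age. No power is given for Hypothesis 3.

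**Correlation over the planned ages.** Assume ages are uniform within each band of 25 subjects.
- Within-band variances: 5.9²/12 = 2.90 and 3.9²/12 = 1.27, mean 2.08.
- Between bands: (13.95 − 8.95)²/4 = 6.25.
- Total 8.33, so SD = 2.89.
- 5.274 × 2.887 = 15.23, squared 231.8. Then r = √(231.8 / (231.8 + 1521)) = 0.36.

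Age stands in for growth here.

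**Unadjusted test with no direct link.** If both volumes depend on growth and on nothing else in common, their correlation is 0.36 × ρ, where ρ is the correlation of gland volume with growth. The documents do not give ρ, so a range is shown. At n = 50, significance at two-sided 0.05 needs |r| above 2.011/√(48 + 2.011²) = 0.279. Simulation with 40,000 trials per setting gives:

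| Assumed ρ | Induced r | Significant, unadjusted |
|---|---|---|
| 0.3 | 0.11 | 12% |
| 0.5 | 0.18 | 25% |
| 0.6 | 0.22 | 33% |
| 0.7 | 0.25 | 44% |
| 0.8 | 0.29 | 54% to 56% |
| 0.9 | 0.33 | 64% |

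Drawing ages uniformly within bands, rather than using a normally distributed growth measure, raises the figures at the top of the table by up to about 3 percentage points.

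**With growth in the model.** Rejection returns to about 5% at every ρ if the covariate captures growth fully. If it measures growth with reliability 0.8 (assumption), rejection is about 6% to 12% for ρ of 0.5 to 0.9, and close to 5% at ρ = 0.3.

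**Price of adjustment.** At ρ = 0.8, collinearity multiplies the standard error of the slope by about 1/√(1 − 0.64) = 1.67. Power of the adjusted test at n = 50 is 29%, 59%, 86% and 98% for partial correlations of 0.2, 0.3, 0.4 and 0.5.

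**The case against.** **The aim is associational.** The experiment and the analysis section speak of relationship and correlation. The study is a pilot, and neither a decision rule nor the sample size rests on Hypothesis 3. A simple regression is a valid description of the marginal association. This stands, and it is why the unadjusted model should be kept. It does not cover the hypothesis itself, which is worded as dependence.

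**The zero-link scenario is a benchmark, not a forecast.** The Abstract pairs loss of acinar volume with loss of secretory capacity, so some direct link is plausible. This also stands. The percentages show how little a significant unadjusted slope would prove. They are not the chance that this study will mislead.

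**Gland volume may mediate the effect of size, so size should not be adjusted for.** That applies when estimating the effect of body size on secretion. For the effect of gland volume, size is a common cause of exposure and outcome, and adjusting for it does not remove a mediator.

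**Adjustment is imperfect and costs power.** Both are true, as the figures above show. They argue for reporting the two slopes side by side, and against letting a non-significant adjusted slope count as a refutation.

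**Conclusion.** The concern holds, as a matter of what the planned regression can support. The unadjusted slope answers whether the two volumes move together. It cannot answer whether secretion depends on gland volume beyond growth. Under the stated assumptions a significant result arises in about 12% to 64% of studies with no direct link, against a nominal 5%. This rests on an assumed ρ of 0.3 to 0.9, on carrying the slope and residual error of CP patients over to healthy children, and on age standing in for growth.

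A reader might infer more than the documents support:
- **That significance is nearly assured.** Using r = 0.63 (the square root of 0.40) gives rates of 97% to 99% at ρ of 0.8 to 0.9. But 0.63 comes from patients with an age SD of 5.816, about twice that of the planned cohort. The same slope and residual error give 0.36 over the planned ages.
- **That Hypotheses 2 and 3 can be told apart for stiffness only in a joint model.** The plan already regresses stiffness on age and size. If Hypothesis 2 is true, size cannot confound stiffness against gland volume, and separate regressions could show one null and one non-null result. A joint model helps but is not the only way.
- **That the stiffness comparison has been dropped.** Exp 3 commits to it. What is missing is the method, which alone is a matter of detail.

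**What to change.** In DATA ANALYSIS/METHODS, under the sub-section on exocrine function, stiffness and parenchymal volume:

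1. Keep the regression of secreted volume on pancreatic volume and label it descriptive.
2. Add a model with age and one body-size measure, such as BSA, as covariates.
3. Report both slopes with 95% confidence intervals, and claim dependence beyond growth only from the adjusted slope.
4. Fit the same two models with MRE stiffness as the outcome, so that Exp 3 has a stated method.
5. State the limited power of the adjusted test, and that a non-significant adjusted slope will not be read as refuting Hypothesis 3.

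The cost is a few sentences and a few regressions. Age, height and weight are already collected. The statistical price is the wider interval for the adjusted slope.
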